5. Data analysis: The primary analysis will be by intention-to-treat. Baseline demographics and secondary outcomes will be compared between RA and O₂ groups using χ^2 , Fisher exact test, Mann-Whitney *U* test, or Student's *t* test as appropriate. The primary outcome, mean maternal and UA MDA, will be compared between groups using the Student's *t* test if normally distributed. If non-normally distributed, the median maternal and UA MDA levels will be compared between groups using the Mann-Whitney *U* test. Linear regression will be used to adjust for relevant covariates. We will perform supplementary analyses including 1) stratified analysis by presence of maternal comorbidities or fetal growth restriction to assess if the effect of O₂ on oxidative stress varies in patients with fetal growth restriction or comorbidities. (2) as-treated analysis to determine whether compliance with the assigned group affects outcomes.
6. Sample size calculation: Based on pilot trial data, the mean UA MDA in 33 patients receiving O₂ for Category II EFM in active labor is $8.3 \pm 2.0 \mu\text{M}$. Assuming a two-sided alpha of 0.05, a total **212 patients (106 O₂ and 106 RA)** will afford 80% power to detect a 10% difference mean UA MDA between O₂ and RA groups, while accommodating for 15% loss due to UA samples. A 10% difference in UA MDA levels may be meaningful as neonatal MDA differences as small as 3-5% are associated with free-radical mediated injuries such as hypoxic ischemic encephalopathy [28, 57] There is limited published data on maternal MDA levels and associated adverse outcomes. However, this sample size will afford >90% power to also detect a 10% difference in maternal MDA between groups. To accommodate a compliance run-in of 6 patients, a total of **218 patients** will be recruited.

Feasibility of the sample size: BJH delivers approximately 4,000 patients per year. Based on results of our pilot trial, 32% of the approached patients meeting eligibility criteria consented to participation in the study. Of the patients enrolled, 40% met criteria for randomization (Category II EFM necessitating intrauterine resuscitation after 6cm dilation). In total, 114 patients were randomized over the study period of 12 months. Therefore, we anticipate successful enrollment of 212 patients within 2.5 years (70-72 patients/year).

Secondary Aim 1:

Investigate the relationship between duration of RA or O₂ exposure and magnitude of oxidative stress

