1. Background, rationale, and hypothesis: The majority of studies investigating MDA concentrations in the pregnant population have utilized serum or plasma samples.⁴⁸ In the non-pregnant population, urinary markers of oxidative stress have been proposed as an alternative to blood because they provide a less invasive way to assess oxidative status, can be used in large-scale studies, and may provide more accurate measurements of oxidative stress than blood because it is less liable to artificial increase of oxidative markers during sample collection and storage.⁴⁹ However, the effect of pregnancy physiology or labor on urine assessment of oxidative stress remains unknown. For example, glomerular filtration rate, renal plasma flow, proteinuria, and glucosuria increase in pregnancy⁵⁰. The effect of these changes in renal physiology on oxidative stress marker analysis is unknown. Furthermore, urine may reflect changes in oxidative stress that are less acute than changes detected in blood (i.e longer time to detect a difference). Given limited data on urine analysis of MDA and 4-HNE in pregnancy and especially during labor, I will study the relationship between MDA and 4-HNE concentrations in paired maternal serum and urine samples to test the hypothesis that urine can serve as a less invasive and readily available alternative to serum to quantify and trend oxidative stress in labor.

2. Data collection: Among patients enrolled in the RCT that are undergoing an induction of labor, urine samples will be collected by study staff at three time points. First, at the time of admission prior to the onset of labor in

order to obtain a baseline assessment of oxidative stress. Second, at the time of randomization in active labor which will be a paired specimen with maternal blood collected at the same time. Third, within 1 hour of delivery which will also be a paired specimen with maternal blood collected at the same time. Urine samples will be collected either as-mid void clean catch specimens or directly obtained from foley catheters in patients with epidurals. Table 2 outlines all planned sample collections in this trial. Urine samples will be centrifuged and stored at -80°C. The same commercially available assays used in Aims 1 and 2 will be used for MDA and 4-HNE quantification. Urine specific gravity will be measured in all samples to account for degree of urine dilution.

Table 2: Timing of all sample collection

| Sample | Time of collection |

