|--------------------------------|--|
| Maternal blood (serum) | -At randomization (active labor with Category II EFM) -Within 1 hour of delivery |
| Umbilical artery blood (serum) | -At delivery |
| Maternal urine | -On admission or at enrollment (prior to labor onset) -At randomization -Within 1 hour of delivery |

3. Outcome and data analysis: The primary outcome is MDA and 4-HNE urine concentrations. The primary outcome will be compared between room air and O₂ groups using Student's t test or Mann-Whitney *U* test, as appropriate. Linear regression will be performed to test the correlation between serum and urine concentrations. The mean MDA and 4-HNE urine concentrations throughout the three time points in labor (Table 3) will be graphed to assess baseline trends in oxidative stress over time within the room air group.
4. Estimated statistical power: Due to the exploratory nature of this aim, we will use a sample size of convenience and perform urine assessments in 100 patients (50 room air and 50 O₂). This aim will only include patients undergoing induction of labor, which comprises 70% of our cohort. These results will provide preliminary data regarding the feasibility of urinary oxidative stress analysis in labor and may allow for future oxidative stress studies to maximize patient participation by limiting invasive blood draws.

Safety Monitoring: The study team will review all neonatal adverse events and establish a data and safety monitoring board (DSMB), which will meet after 50% of participants have been recruited to review any adverse neonatal or maternal events among the study cohort and determine safety of continuing the study to completion. Reportable severe adverse neonatal outcomes include intrapartum stillbirth and neonatal death. Reportable non-severe adverse neonatal outcomes include need for hypothermia protocol, seizures, and prolonged NICU stay >72 hours. The study statistician will perform an interim analysis after 50% recruitment. The Haybittle-Peto stopping rule will be used in which a *p* <0.001 for the difference in the primary outcome between groups will guide further conduct of the trial.

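### Secondary Aim 2 hypothesises that urine can stand in for serum, but its only serum–urine analysis tests for a non-zero correlation, which can show association and not substitutability

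*Combined protocol and SAP*

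**What the plan says.** All references are to the combined protocol and SAP, Secondary Aim 2, unless stated otherwise.

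- **Hypothesis (item 1, Background, rationale, and hypothesis):** "urine can serve as a less invasive and readily available alternative to serum to quantify and trend oxidative stress in labor".
- **Samples (item 2, Data collection, and Table 2):** urine is taken on admission, at randomization and within 1 hour of delivery. The last two are paired with maternal blood; on the randomization sample the text reads "Second, at the time of randomization in active labor which will be a paired specimen with maternal blood collected at the same time". Specific gravity is measured to allow for dilution, but the plan does not say how it enters the analysis.
- **Analysis (item 3, Outcome and data analysis):** three things are planned. Urine levels are compared between arms: "The primary outcome will be compared between room air and O₂ groups using Student's t test or Mann-Whitney *U* test, as appropriate". Serum and urine are related by regression: "Linear regression will be performed to test the correlation between serum and urine concentrations". Mean urine values over the three time points are graphed in the room air group.
- **Size and status (item 4, Estimated statistical power):** 100 patients, 50 per arm, chosen by convenience, with the reason given as "Due to the exploratory nature of this aim". The results are described as preliminary feasibility data that "may allow for future oxidative stress studies to maximize patient participation by limiting invasive blood draws".

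No alpha, minimum correlation, R², prediction-error limit, within-woman change analysis or success criterion is given for this aim.

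**The concern.** The hypothesis has two parts, and the regression addresses neither fully.

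- **Quantify.** To use urine in place of serum, one must be able to recover the serum value from the urine value with tolerable error. A test that the slope is not zero asks only whether there is any linear relation at all.
- **Trend.** Tracking oxidative stress means that when a woman's serum value moves, her urine value moves with it. Correlating levels across women does not show this. The plan's own background section notes that urine may respond more slowly than blood.

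At stake is the later use named in the plan: studies that take fewer blood samples on the strength of this aim. If a significant correlation were read as support for substitution, those studies could rest on a marker that says little about the blood value.

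**Working it through.** The plan gives no power figure or detectable correlation for this aim, so there is nothing of its own to reproduce.

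**Inputs.** n = 100 patients, 50 per arm (item 4). Two paired time points per patient (item 2). Pilot maternal MDA SD 1.0 µM (Primary Aim 1, Rationale). Two-sided alpha 0.05 is an assumption: the plan states it only for the main sample size ("Assuming a two-sided alpha of 0.05", Primary Aim 1, Sample size calculation).

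**Step 1: smallest significant correlation.** The slope test in simple regression is the same test as that of r = 0, so r_crit = t / √(n − 2 + t²), with t on n − 2 degrees of freedom. For n = 100, t = 1.984 and r_crit = 1.984 / √(98 + 3.94) = 0.197.

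**Step 2: what that correlation means.**
- R² = 0.197² = 3.9%.
- The residual SD of serum given urine is √(1 − 0.039) = 0.98 of its unconditional SD.
- With SD 1.0 µM, the 95% prediction half-width falls from 1.96 to 1.96 × 0.98 = 1.92 µM.
- The 95% CI for r is about 0.00 to 0.38.
- Under bivariate normality, urine and serum fall on the same side of their medians with probability ½ + arcsin(0.197)/π = 56%, against 50% by chance.

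**Step 3: how often a weak relation is significant.** By Fisher z, power = Φ(atanh(ρ)·√97 − 1.96). This is 51% at ρ = 0.2, 80% at ρ = 0.277 and 86% at ρ = 0.3, where 9% of variance is explained.

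**Step 4: sensitivity to what the plan leaves open.**

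| Variant | r_crit | R² |
|---|---|---|
| 100 pairs, two-sided 0.05 | 0.197 | 3.9% |
| 100 pairs, one-sided 0.05 | 0.165 | 2.7% |
| 100 pairs, alpha 0.0125 (2 markers × 2 times) | 0.249 | 6.2% |
| 85 pairs (15% loss, assumed) | 0.213 | 4.5% |
| One arm, 50 pairs | 0.279 | 7.8% |
| 200 pairs treated as independent | 0.139 | 1.9% |

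In every variant the test can be significant with less than 8% of variance explained.

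**Step 5: levels and changes can part company.** As an illustration, let serum = B + e and urine = B + f. B is a woman's stable level with variance 2; e and f are independent from each other and over time, each with variance 1. The correlation of levels is 2/(2 + 1) = 0.67. In the change scores B cancels, leaving e₂ − e₁ and f₂ − f₁, whose correlation is 0. A strong level correlation is compatible with no tracking at all.

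**Step 6: precision of estimation at the planned size.** The Fisher z interval is tanh(atanh(r) ± 1.96/√(n − 3)). An observed r of 0.8 gives 0.72 to 0.86 with one estimate from n = 100, and 0.67 to 0.88 from one arm of 50. Adjusting for arm costs one degree of freedom (SE 1/√96 = 0.102 instead of 1/√97 = 0.102), which is negligible. A single arm-adjusted estimate is therefore preferable to two separate ones.

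**The case against.** The strongest reply is that the plan never says what a significant correlation would lead to. A reader might infer that p < 0.05 will be taken as proof that urine can replace blood. The documents contain no such rule, and regression also yields a slope, R² and residual error, so nothing confines the report to a p-value. This stands: the gap is a missing criterion, not a stated wrong one.

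Second, the aim is titled as a study of the relationship between the two fluids, is labelled exploratory, and promises only preliminary feasibility data. This also stands and limits the weight of the point. It excuses the absence of a power calculation. It does not make a test of association an answer to a substitution hypothesis.

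Third, urine would not be judged on the regression alone. The between-arm comparison bears on whether urine detects the exposure effect, and the room air graph shows urine over time. Both are useful, but neither sets urine against serum.

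Fourth, a reader might infer that the two time points or the arms are pooled in the regression. The plan does not say so, and the 0.139 above applies only if they are.

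Finally, a fixed bar such as a lower confidence limit above 0.7 is tempting but has no source in the documents. At a true correlation of 0.80 it would be passed 62% of the time with n = 100 and about 35% with a single arm of 50. Noise in change scores also lowers what can be seen. If each fluid has reliability 0.9 and a between-time correlation of 0.5 to 0.7 (assumed), the reliability of the change is (0.9 − 0.5)/(1 − 0.5) = 0.80 to (0.9 − 0.7)/(1 − 0.7) = 0.67. Even perfect tracking would then show r of only about 0.67 to 0.80. This stands, and no threshold is prescribed below.

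**Conclusion.** The mismatch is real. The hypothesis is substitution, for level and for trend; the planned serum–urine analysis can establish only association, and it leaves within-woman change unexamined. At 100 pairs it is significant from r of about 0.20, or 4% of variance. Across the variants considered, the figure runs from 1.9% to 7.8%. The calculation rests on a two-sided alpha of 0.05 carried over from the main sample size and, in the main case, on one pair per patient.

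The effect is confined to the interpretation of this exploratory aim and to later studies that might build on it. A reader might infer that the trial's main result is weakened. It is not: the primary outcome is maternal and umbilical artery MDA and 4-HNE in blood and does not depend on this analysis. The change is worth making because it is cheap and uses samples already planned.

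**What to change.** In Secondary Aim 2, item 3, replace the test of correlation with estimation, for MDA and 4-HNE separately:

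1. At each paired time point (randomization and delivery), report the serum–urine correlation after adjustment for dilution, with its 95% CI, R² and the prediction error for serum given urine. State how specific gravity is used.
2. From the same pairs, report the correlation between the within-woman change in urine and the change in serum (delivery minus randomization), adjusted for arm. This is one estimate pooled within arms, n about 100, with its 95% CI.
3. State that a significant non-zero correlation alone will be reported as 'associated, not shown to be interchangeable'.
4. If the sponsor wishes to claim substitution, it should set and justify a minimum value in advance, allowing for assay noise in change scores.

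The cost is analysis wording and slightly more analysis; samples and assays are unchanged. The downside is that a positive conclusion about substitution becomes harder to reach.

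### Secondary Aim 2 relates urine to serum by a plain linear regression that does not say how two pairs per woman, time point and arm are handled, and so does not isolate whether urine tracks serum within a woman

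*Combined protocol and SAP*

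**What the plan says.** Secondary Aim 2, item 1, sets the hypothesis that "urine can serve as a less invasive and readily available alternative to serum to quantify and trend oxidative stress in labor". Item 2 provides two blood-urine pairs per woman: one "at the time of randomization in active labor which will be a paired specimen with maternal blood collected at the same time", the other "within 1 hour of delivery which will also be a paired specimen with maternal blood collected at the same time". The admission urine has no paired blood (Table 2).

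Item 3 gives the analysis of the relationship: "Linear regression will be performed to test the correlation between serum and urine concentrations". It does not name the outcome and the predictor, the time point or points used, the unit of analysis, any covariates or a variance method. The only restriction by arm in this item concerns a graph of urine means, drawn "to assess baseline trends in oxidative stress over time within the room air group". Specific gravity is measured in every urine sample (item 2), but its place in the regression is not stated.

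Item 4 takes 100 women, 50 per arm: "Due to the exploratory nature of this aim, we will use a sample size of convenience". The sentence on covariate adjustment under Primary Aim 1, item 5, belongs to that aim and names no covariates.

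**The concern.** Three features of the design matter to this regression, and the sentence addresses none of them.

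- **Woman.** Two pairs from one woman are not independent. Ordinary regression on up to 200 pairs would count them as if they were.
- **Arm and time.** The trial expects O₂ to raise maternal markers. If O₂ raises both serum and urine, the two fluids correlate across the arms even when there is no link within an arm. A shift in both fluids during labor does the same when the time points are pooled.
- **The question.** Trending is about change within a woman. A pooled regression mixes differences between women with changes within them, and a single-time-point regression sees only differences between women.

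Item 4 hopes that the results may let later studies limit blood draws. A correlation that is too precise, or that comes from the arm contrast, would give that idea more support than it has earned.

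**Working it through.** **No plan figure to reproduce.** This aim has a convenience sample and no stated power or detectable correlation.

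**Inputs from the plan.** 100 women, 50 per arm, two pairs each. Pilot maternal MDA is 6.5 µM ± 1.0 (Primary Aim 1, item 2), with the ± read as an SD. The trial's 10% maternal difference (item 6) is then 0.65 µM, or 0.65 SD.

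**Assumptions, not in the plan.** Within-woman correlation (ICC) of 0.3 to 0.9, equal in serum and urine. O₂ effect of 0.65 or 1.0 SD, equal in both fluids. Simulations in steps 1 to 3 used 20,000 runs per setting, with no serum-urine link within arm and time point.

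**Step 1. Both pairs pooled, no O₂ effect.** With two pairs per woman, the true variance of the slope is about 1 + ICC_serum × ICC_urine times the variance that ordinary regression reports. The rejection rate at nominal 5% is 2 × [1 − Φ(1.96 / √(1 + ICC²))].

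| ICC, both fluids | 1 + ICC² | Reported / true SE | Rejection, formula | Rejection, simulated |
|---|---|---|---|---|
| 0.3 | 1.09 | 0.96 | 6.0% | 6.3% |
| 0.5 | 1.25 | 0.89 | 8.0% | 8.1% |
| 0.7 | 1.49 | 0.82 | 10.8% | 11.1% |
| 0.9 | 1.81 | 0.74 | 14.5% | 14.9% |

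If only serum is correlated within woman (0.7, urine 0), the rate is 5.0%. If each time point is analysed separately, it stays at about 5%.

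**Step 2. Both pairs pooled, shared time shift.** A shift of 0.65 SD in both fluids, with no O₂ effect and ICC 0.5, gives r of about 0.10 and 29% significant results.

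**Step 3. Delivery pair only, both arms, no arm term.** With half the women on O₂ and a shift of d SD in both fluids, the correlation made by arm alone is r = 0.25d² / (1 + 0.25d²).

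- d = 0.65: 0.1056 / 1.1056 = 0.10; simulated significant results 16%.
- d = 1.0: 0.25 / 1.25 = 0.20; simulated 52% to 53%.

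With both time points pooled, a quarter of the pairs are O₂-exposed, so 0.25 × 0.75 = 0.1875 replaces 0.25. Then r is 0.07 and 0.16, with 18% to 20% and 61% to 62% significant for ICC 0 or 0.5. The randomization pair alone gives r = 0, because O₂ has not yet been given. If O₂ moves serum only, r is also 0.

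**Step 4. Candidate remedies, ICC 0.5, O₂ shifting both fluids.**

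| Model | 0.65 SD | 1.0 SD |
|---|---|---|
| Change on change, no arm term | about 17% | about 54% |
| Both pairs, additive arm and time, woman-clustered SEs | about 8% | about 13% |
| Change on change with arm term | about 5–6% | about 5–6% |
| Both pairs, arm, time and arm-by-time, woman-clustered SEs | about 5–6% | about 5–6% |

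O₂ acts only after the first pair, so its effect is an arm-by-time effect. Additive terms do not remove it, and neither does taking differences without an arm term.

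**The case against.** The text does not say that the pairs are pooled. One regression per time point fits the wording as well and has no standard-error problem. This stands: a reader might infer that the plan commits to one ordinary regression on 200 pairs with standard errors that are too small, and the document does not support that. The problem also needs within-woman correlation in both fluids, for which the plan gives no figure.

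The correlation made by O₂ is small at the trial's own maternal target. An r of about 0.10 is well below the r of about 0.28 that 100 women could detect with 80% power, and would hardly justify replacing blood with urine. The O₂ effect on urine is assumed, and item 1 itself warns that urine may respond less acutely than blood. This stands as a limit on size.

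A joint rise in both fluids after O₂ is itself a shared within-woman change, so it can be read as evidence that urine responds as serum does. That is fair, and it makes this partly a matter of what is to be estimated. But item 3 already compares urine between arms, which addresses the group response. Whether a woman's urine follows her own serum beyond that response is a separate question, and the regression sentence does not separate the two.

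Finally, a reader might infer that this aim decides whether later trials can drop blood draws. Item 4 claims only preliminary feasibility data, and no sample size or primary conclusion rests on it.

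**Conclusion.** The point holds as a conditional one. The plan collects the two pairs per woman needed to study tracking, but states a plain regression that leaves woman, time and arm open, and nothing elsewhere in the document closes the gap.

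- If the pairs are pooled, false positives run at about 6% to 15% for assumed ICC 0.3 to 0.9 in both fluids; a shared time shift adds to this.
- If only the delivery pairs are used across both arms, O₂ alone can give about 16% significant results (r about 0.10) at an assumed 0.65 SD shift in both fluids, and about 52% (r about 0.20) at 1.0 SD. The larger shift exceeds the trial's own maternal target.
- On either reading, the within-woman association is not isolated. This part does not depend on the assumed figures.

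The consequence is minor, because the aim is exploratory, but the improvement uses data already planned.

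**What to change.** In Secondary Aim 2, item 3, state for each marker that the change in specific-gravity-corrected urine from randomization to delivery will be regressed on the change in serum over the same interval, with a term for arm. Report the slope with its confidence interval as the within-woman result.

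If both pairs enter one model, use a random intercept per woman or woman-clustered standard errors. Include time, arm and arm-by-time terms, and split serum into each woman's mean and her deviation from it, so that the between-woman and within-woman effects are reported separately.

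The cost is a few lines of analysis-plan text and no new samples or visits. Confidence intervals will be somewhat wider, and the change model uses only women with both pairs.

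### The urine trend over labor is assessed only by a graph of three means, so the plan gives no estimate of within-woman change and no interval

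*Combined protocol and SAP*

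**What the plan says.** Secondary Aim 2, item 1 (background and hypothesis) proposes that urine can serve as a less invasive and "readily available alternative to serum to quantify and trend oxidative stress in labor". Item 2 (data collection) restricts the aim to women having labor induced and states that "urine samples will be collected by study staff at three time points": on admission before labor, at randomization, and within 1 hour of delivery. The last two are paired with maternal blood; the first is not. Specific gravity is measured in every urine sample to allow for dilution.

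Item 3 (outcome and data analysis) gives three analyses of the urine data:

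- A comparison between arms: "The primary outcome will be compared between room air and O₂ groups using Student's t test", or the Mann-Whitney test.
- A serum-urine analysis: "Linear regression will be performed to test the correlation between serum and urine concentrations".
- The trend: mean urine MDA and 4-HNE at the three time points "will be graphed to assess baseline trends in oxidative stress over time within the room air group". (It cites Table 3, but the collection times are in Table 2.)

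Item 4 sets the size at 100 women, 50 per arm: "Due to the exploratory nature of this aim, we will use a sample size of convenience". For urine, the plan states no within-woman model, no estimate of change, no interval and no rule for missing samples.

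**The concern.** Trending is part of the stated hypothesis, and each woman is sampled three times so that change can be seen. A plot of three means shows a direction but does not say how large the change is or how well it is known. Neither of the other two urine analyses fills the gap. The between-arm test is not an analysis of change over time, and the regression relates serum to urine. The admission sample has no paired serum and precedes randomization, so the plot is the only stated analysis that uses it as the pre-labor baseline it was collected to provide.

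Two things are at stake. A reader shown only group means cannot recover the precision of the within-woman change and may judge it as if three separate groups of women had been sampled. And if some women lack a sample, a different set of women stands behind each plotted point, so the line may move for that reason alone. The plan expects this aim to supply preliminary data for later studies, which need an estimate and its uncertainty.

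**Working it through.** **The plan's own figure.** The 100 women are a convenience sample, so there is no calculation to reproduce. The number is feasible on the plan's figures: 70% inductions × 212 = about 148.

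**Inputs.** From the plan: 50 room air women and three samples each. Not in the plan, hence assumed: within-woman correlation r of 0.3, 0.5 or 0.7, with results in units of the between-woman SD at one time point; and 15 to 30% of post-delivery urine samples missing. The only sample-loss figure in the plan is 15%, and it is for umbilical artery blood.

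**Step 1: point trend, complete samples.** The difference between two plotted means equals the mean of the within-woman differences. The plotted trend is therefore not biased; what is lacking is its precision.

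**Step 2: precision of a change between two time points.**

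- Within-woman: half-width = t(49) × √(2(1 − r)/50), with t(49) = 2.010.
- Means read as independent: half-width = t(98) × √(2/50) = 1.984 × 0.200 = 0.397 SD.

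| r | Within-woman half-width (SD) | Independent reading (SD) | Independent reading is wider by |
|---|---|---|---|
| 0.3 | 0.336 | 0.397 | 18% |
| 0.5 | 0.284 | 0.397 | 40% |
| 0.7 | 0.220 | 0.397 | 80% |

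Put the other way, the within-woman interval is 15 to 45% narrower.

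**Step 3: missing samples.** The plotted mean shifts by (fraction missing) × (mean difference between women with missing and observed samples). For a difference of 0.5 to 1 SD, that is 0.15 × 0.5 = 0.075 to 0.15 × 1 = 0.15 SD at 15% missing, and 0.15 to 0.30 SD at 30% missing.

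A simulation with 50 women, no true change and equal correlation between time points made the post-delivery sample missing under three mechanisms. In the first and third, the log-odds of being missing rose by 1 per SD. Correlation was 0.5 to 0.7 and 15 to 30% were missing. The likelihood-based estimate was represented by regressing the third value on the first two among observed women and averaging the prediction over all women.

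| Missingness depends on | Plotted means | Likelihood-based estimate |
|---|---|---|
| Earlier, observed values | false fall of 0.07 to 0.18 SD | within about 0.005 SD of zero |
| Nothing (completely at random) | about 0 | about 0 |
| The unobserved post-delivery value | also biased | false fall of 0.06 to 0.18 SD |

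Under the first mechanism with r = 0.3, the false fall in the plotted means is smaller, 0.04 to 0.08 SD. Simple differences restricted to complete pairs are not a dependable substitute: under the same mechanism, over correlations of 0.3 to 0.7, they showed a false rise of up to about 0.18 SD.

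**The case against.** The strongest reply is that this is a descriptive plot in an aim that calls itself exploratory. The aim's title concerns the relationship between serum and urine markers, and the regression addresses that. A urine-only model in the room air arm would not show that urine follows change in serum. This stands: it limits the weight of the point. It does not remove it, because trending is named in the hypothesis and preliminary data are of little use for planning without an interval.

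A reader might infer more than the documents support, in four ways:

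- **That the plot gives a wrong trend because it ignores pairing.** With complete samples it does not (Step 1).
- **That the plan proposes an unpaired interval across time points.** It proposes none; 0.40 SD describes only how the plot might be misread.
- **That missing urine samples will produce a false trend.** That needs missingness related to the marker level. The plan gives neither a urine loss rate nor a reason to expect such a link, and the Overview allows catheter, straight-catheter or clean-catch collection, which should limit losses.
- **That a mixed model settles the missing-sample problem.** It does so only if missingness depends on observed values.

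Dilution also matters. The Overview lists intravenous fluid bolus among the other resuscitation techniques, so a narrow interval around uncorrected concentrations could partly reflect hydration. Specific gravity therefore belongs in any repair.

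**Conclusion.** The point holds as a gap in reporting and precision, not as an error in the plotted trend. As written, the plan will yield three means per marker, with no estimated change and no interval, from data that could supply both. On assumed correlations of 0.3 to 0.7, reading the means as independent would make the uncertainty look 18 to 80% larger than it is. A false fall of 0.07 to 0.18 SD is possible but conditional on level-related missingness at the assumed rates and correlations; it is not something the documents predict. Every SD-unit figure rests on assumptions, since the plan gives no urine SD, correlation or loss rate. Priority is low: no primary, confirmatory or safety result is touched.

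**What to change.** In Secondary Aim 2, item 3:

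1. Keep the plot, and add individual women's lines and the number of samples at each time point.
2. Add, as the trend analysis, a linear mixed model in the room air women for each marker: (log) urine concentration on time point as a category, with a random intercept for woman, using all available samples.
3. State how the specific gravity already measured enters the model.
4. Report the admission-to-randomization and randomization-to-delivery changes with 95% CIs, labeled exploratory.
5. State that the model removes bias from missing samples only when missingness depends on observed values.
6. Correct the table reference.

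The cost is a few sentences of analysis plan and a few lines of code, so slightly more analysis work. No new samples, assays or participants are needed.
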